## **Study Population**

The study population will be composed of volunteers between the ages of 18 and 65 and will include 30 total subjects. Recruitment will be via an email to the Department of Anesthesia at the University of Arkansas for Medical Sciences asking for volunteers to participate in the study. In order to minimize coercion, it will be emphasized that participation is voluntary and that there is no reward or negative consequence for participating or not. A total of 2 reminder emails will also be sent 1 week apart from each other and the initial recruitment email. No recruitment will occur in person to avoid potential pressure from a colleague/peer.

## Inclusion Criteria

• Age between 18-65

PI: [name]

## **Exclusion Criteria**

• History of diabetes, delayed gastric emptying, previous gastric surgery, lactose intolerance, currently pregnant, consumption of solid/liquids in 6 hours prior to commencement of ultrasound study

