# **Background and Rationale**

An important component in the pre-operative patient evaluation is to establish the duration of time a patient has been fasting in order to reduce the risk of pulmonary aspiration. An inadequate fasting time may prompt a change in anesthetic plans or result in the delay or cancellation of a case altogether. The risk of anesthetic-related pulmonary aspiration is rare due to current anesthetic practices, with the incidence in adults cited around 0.05% or less. However, the sequelae of aspiration can lead to aspiration pneumonitis, prolonged mechanical ventilation and unanticipated intensive care.

There is no established gastric volume definitively known to increase anesthetic risk of aspiration but it has been observed that the gastric volume in most healthy, fasted patients can be up to 1.5 ml/kg.

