Current guidelines recommend a minimum fasting period of 8 hours for fatty foods, 6 hours for nonhuman milk and non-fatty solid foods, and 2 hours for clear liquids. Acceptable examples of clear liquids include water, black coffee or tea, carbonated beverages, and fruit juices without pulp. However, about 68% of adults in the United States consume coffee with add-ins such as cream and/or sugar. One study by Larsen et al. found that adding up to 50% full fat milk to coffee led to no or minimal increase in gastric volume measured by Magnetic Resonance Imaging after 2 hours. Hillyard et al.8 examined the addition of milk to tea and found no difference in gastric emptying times using the paracetamol absorption technique and ultrasound measurement of the gastric antrum. These studies provide some useful insight on gastric emptying times but are not generalizable to beverage consumption in the United States. Typically, the volume of coffee consumed is larger than that in Europe and half and half is preferred to milk. Half and half is a mixture of milk and cream and has a fat content ranging from 10.5-18% compared to 3.25% fat in whole milk.9 Non-dairy coffee creamer is another popular addition to coffee, which consists of vegetable oil and corn syrup. This adds both fat and sugar to coffee. Therefore, the effects of larger quantities of coffee with the addition of high fat content milk products on gastric emptying is unknown. We propose a volunteer cross-over study in healthy individuals to assess the effects of milk additives to coffee and its effects on gastric emptying. In this study we will compare two separate additions to the coffee using half and half and liquid non-dairy coffee creamer.

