# **Data Analysis**

Point of care bedside ultrasound will be used to measure the cross-sectional area of the gastric antrum of participants at baseline prior to consumption of coffee and 2 hours after consumption of coffee. Three measurements will be taken and recorded each time and the mean of these measurements will be used to calculate the predicted gastric volume. The difference between gastric volume at baseline and after coffee consumption will be compared across all three study arms. We will analyze the data using standard statistical methods such as mean, median, mode, standard deviation and statistical significance. We will also determine if the gastric volumes after consumption of coffee in each arm exceeds 1.5 ml/kg.

PI: [name]

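### The study is meant for healthy people and uses a reference volume from healthy, fasted patients, but the criteria set no general health requirement and ignore medicines that alter gastric emptying.

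*Combined protocol and SAP*

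**What the plan says.** The Background and Rationale states the intended population: "We propose a volunteer cross-over study in healthy individuals to assess the effects of milk additives to coffee". The same section supplies the reference volume, reporting that "gastric volume in most healthy, fasted patients can be up to 1.5 ml/kg". The Data Analysis section then uses that figure: "We will also determine if the gastric volumes after consumption of coffee in each arm exceeds 1.5 ml/kg".

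The operative sections are looser. Study Population says "The study population will be composed of volunteers between the ages of 18 and 65" and does not require them to be healthy. Inclusion Criteria has one entry, "Age between 18-65". Exclusion Criteria lists "History of diabetes, delayed gastric emptying, previous gastric surgery, lactose intolerance, currently pregnant", and then only food or drink taken within 6 hours of the scan.

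The appended Data Collection Form has columns for study number, session, age, gender, height, weight, BMI, two times and the antral areas. It has none for medicines or medical history.

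**The concern.** The outcome is gastric volume two hours after a drink, so anything that slows or speeds emptying acts on it directly. By listing diabetes, delayed emptying and gastric surgery, the exclusions show that the investigators already regard altered emptying as a threat. A medicine with the same effect is the same threat by another route, and the criteria do not address it. Someone applying the criteria exactly could therefore enrol a volunteer outside the population described in the Background.

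What is at stake is chiefly the statement about 1.5 ml/kg. It compares an absolute volume with a figure taken from healthy people, so comparing each participant with themselves gives it no protection. A medicine that slows emptying could push a participant over the line for reasons unrelated to coffee, and one that speeds emptying could hide an exceedance.

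The gap also cannot be closed afterwards. The form does not capture medicine use, and Data Handling and Recordkeeping says the data cannot be linked back to individuals. An outlying volume could not later be traced to a medicine.

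**Working it through.** The plan gives no figure to reproduce here. It states 30 participants with no derivation, and this point does not depend on one. The check is first textual, then a short calculation of size.

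**Text side by side**

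| Element | Intended (Background, Data Analysis) | Required (Inclusion, Exclusion, form) |
|---|---|---|
| Health | Healthy individuals | Age 18 to 65 and a short list of excluded conditions |
| Reference | 1.5 ml/kg, from healthy, fasted patients | Fasting for 6 hours is required; general health is not |
| Medicines altering emptying | Not mentioned | Not mentioned, and not recorded |

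Fasting is carried from the reference into the criteria. Health is carried over only in part.

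**Weight of one participant in the 1.5 ml/kg check.** The plan does not say how this check is summarised. Assume it is the proportion of participants above the line in each arm. With n = 30 from Study Population, one participant is 1/30 = 0.033, or 3.3 percentage points. A participant over the line after all three drinks because of a medicine would add that much to every arm, which is the worst case per person.

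**Chance that the issue arises.** The documents give no prevalence, so p is assumed. The chance of at least one user among 30 is 1 − (1 − p)^30, and the expected number is 30p.

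| Assumed p | Chance of at least one | Expected number |
|---|---|---|
| 1% | 1 − 0.99^30 = 26% | 0.3 |
| 2% | 1 − 0.98^30 = 45% | 0.6 |
| 5% | 1 − 0.95^30 = 79% | 1.5 |
| 10% | 1 − 0.90^30 = 96% | 3.0 |

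**Effect on the comparison between drinks.** The analysis compares change from baseline across arms within the same people.

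- Stable use: if the medicine adds the same amount s to a participant's change after every drink, the contrast of drinks A and B is (A + s) − (B + s) = A − B, and s cancels. If medicine and drink do not act additively, the cancellation is only partial.
- Use at one session only, unrelated to the drink, adding d to that session: if all drink orders are equally likely, each drink has a one-third chance of being the affected one. The expected contribution to the contrast A − B is (1/3)(+d) + (1/3)(−d) + (1/3)(0) = 0. The effect is extra variance with no expected direction.
- Size of one such realisation: d/30 on the mean difference. For an assumed and deliberately large d of 100 ml, that is 100/30 = 3.3 ml, in either direction. The documents give no standard deviation against which to judge it.

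**The case against.** A reader might infer that the comparison of the three drinks, which is the stated objective, is biased. The documents do not support that. Each participant takes all three drinks, the outcome is change from a baseline scan in the same session, and drink order comes from a random number generator. As shown above, stable use largely cancels and sporadic use unrelated to the drink adds noise with no expected direction. This part of the objection stands.

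A reader might also treat the 1.5 ml/kg check as a formal safety conclusion. The Background says that no gastric volume has been established as raising aspiration risk, the check is introduced as an additional analysis, and it is absent from the Objectives. It is a secondary description, which limits the damage. This too stands.

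Three further defences hold in part:

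- The exclusions already make health partly operational. The entry on delayed gastric emptying is not confined to disease, so a recognised drug-induced delay could be read as covered. Unrecognised delay and medicines that speed emptying would still pass.
- Each session has a fasted baseline scan, so a volunteer with a high fasting volume would be visible. Slow emptying of a drink with a normal baseline would not be.
- Excluding medicine users narrows the study relative to the pre-operative patients who motivate it. That is a fair cost, but the plan itself chose healthy individuals.

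Finally, neither the prevalence nor the size of any drug effect comes from the documents. The textual mismatch does not depend on them.

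**Conclusion.** The point holds as a moderate, cheaply corrected gap. The Background and the 1.5 ml/kg reference presuppose healthy people, while the criteria enforce this only through a few named conditions, say nothing about medicines that alter emptying, and leave no record from which users could be identified.

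The main consequence is for the 1.5 ml/kg check: up to 3.3 percentage points of an arm's proportion per affected participant, assuming a proportion is what will be reported and that the medicine changes which side of the line the participant falls on. Whether anyone is affected is unknown; over assumed prevalences of 1% to 10%, the chance of at least one user runs from 26% to 96%. For the drink comparison the consequence is mainly avoidable variance, assuming that medicine use is unrelated to the drink and that all orders are equally likely. It is not a reason to doubt the design of that comparison.

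**What to change.** Reconcile Inclusion Criteria and Exclusion Criteria with the Background:

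1. Make being healthy an eligibility rule.
2. Add an exclusion for current use of medicines known to alter gastric emptying and for known disease affecting gastric emptying. The investigators should define the list, since that is a clinical judgement.
3. Add a yes/no medicine-use field to the Data Collection Form, asked at every session, because eligibility at entry does not cover use that begins later.
4. State in Data Analysis that the 1.5 ml/kg summary and the drink comparison will be repeated without any session in which such use is reported. A participant with one session removed then informs only the contrast between the other two drinks.

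The cost is one or two lines of criteria, one form field and a short question per session, with no test or extra visit. The downside is a slightly smaller pool, which matters somewhat because all 30 volunteers come from one department, and slightly narrower generalisability. The question has to be in place before enrolment, since the answers cannot be recovered once the data are anonymised.

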# **Risks and Benefits**

A risk to study participants is the potential for loss of confidentiality of study data. Measures to protect the confidentiality of study data will be implemented as described in the Data Handling and Recordkeeping section below.

There are no direct benefits to participants.

# Data Handling and Recordkeeping

The Principal Investigator will carefully monitor study procedures to protect the safety of research subjects, the quality of the data and the integrity of the study. De-identified data will be initially recorded on paper on a data collection form then transcribed to Excel and kept on UAMS-maintained servers. The paper records will be destroyed by confidential shredding. All collected data will be completely anonymized with no way to relink it to individual participants. Each participant will be assigned a unique study number which will not be associated with any identifying information. This study number will be used each time the participant returns for the next study measurement. Only investigators will have access to the collected data. At the conclusion of the study, the data which is permanently de-identified will be retained for seven years after completion of the project.

# **Data Analysis**

Point of care bedside ultrasound will be used to measure the cross-sectional area of the gastric antrum of participants at baseline prior to consumption of coffee and 2 hours after consumption of coffee. Three measurements will be taken and recorded each time and the mean of these measurements will be used to calculate the predicted gastric volume. The difference between gastric volume at baseline and after coffee consumption will be compared across all three study arms. We will analyze the data using standard statistical methods such as mean, median, mode, standard deviation and statistical significance. We will also determine if the gastric volumes after consumption of coffee in each arm exceeds 1.5 ml/kg.

PI: [name]

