## **Objectives**

The primary objective of this study is to compare gastric volume using bedside ultrasound in volunteers 2 hours after consumption of black coffee, coffee with half and half, and coffee with non-dairy creamer.

PI: [name]

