## Study Design and Procedures (sometimes called "Methods")

This study is a randomized controlled crossover study with 3 arms. One arm is the consumption of a 12 ounce (354.8 ml) brewed black coffee. The second is a 12 ounce brewed black coffee plus 1 ounce (30 ml) of half and half. The third arm is a 12 ounce brewed black coffee plus 1 ounce (30 ml) of non-dairy coffee creamer. Each subject will participate in all 3 arms of the study and serve as their own control.

The order of which arm they will be assigned to will be determined by a computerized random number generator which will create a unique sequence from 1 to 3. The number 1 will be attributed to black coffee without additives. The number 2 will be attributed to coffee with half and half and the number 3 will be attributed to coffee with non-dairy coffee creamer. For example, a random generation of the sequence 2 1 3 will result in the order of arms to be coffee with half and half, black coffee, then coffee with non-dairy creamer. The investigator performing the gastric ultrasound will be blind as to which drink was consumed. In order to maintain blinding and anonymization during the study, each participant will be assigned a unique study number which will not be associated with any identifying information. This study number will be associated with the randomized number sequence of their coffee arm order and will be used each time the participant returns for the next study measurement.

Each study participant will be instructed to consume nothing by mouth for at least 6 hours prior to the commencement of the study. An investigator will measure the cross-section of the gastric antrum using bedside ultrasound with the participant in the right lateral decubitus position as a baseline measurement. The participant will then consume one of the 3 prepared coffee options. They will be instructed to return 2 hours post consumption for the investigator to repeat the gastric antrum cross-section measurement with ultrasound. There must be a minimum of 2 days between repeat measurements with the other arms of the study.

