# Study: How do you take your coffee before anesthesia? Data Collection Form

Date: \_\_\_\_\_

ID #	Session #	Age	Gender	Height	Weight	BMI	Time coffee consumed	Time US exam	Baseline Antrum CSA			Post coffee Antrum CSA

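### The primary objective is 2-hour gastric volume, but the only planned between-arm comparison is raw change from baseline, which can lose precision that a baseline covariate would recover

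*Combined protocol and SAP*

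**What the plan says.** The Objectives section states: "The primary objective of this study is to compare gastric volume using bedside ultrasound in volunteers 2 hours after consumption of black coffee", and goes on to name the two coffee-with-additive drinks. The outcome there is the volume at 2 hours; change is not mentioned.

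Data Analysis plans one comparison between arms: "The difference between gastric volume at baseline and after coffee consumption will be compared across all three study arms". It uses the 2-hour volume on its own only for a threshold check within each arm: "We will also determine if the gastric volumes after consumption of coffee in each arm exceeds 1.5 ml/kg". The methods are given as "standard statistical methods such as mean, median, mode, standard deviation and statistical significance". No test, model, covariate or significance level is named, and neither document section designates a primary endpoint.

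The baseline is available. Study Design and Procedures has the antrum scanned before the drink, "with the participant in the right lateral decubitus position as a baseline measurement". The Data Collection Form has a session number, a baseline antrum CSA field and a field for "Post coffee Antrum CSA". The same design section has every participant take all three drinks in random order, and it separates the sessions: "There must be a minimum of 2 days between repeat measurements with the other arms of the study".

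**The concern.** The objective and the analysis name different outcome variables, and nothing says which one carries the main result.

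The choice of raw change also has a statistical price. In this crossover, comparing drinks within participant already removes stable differences between people. Subtracting the session's baseline helps only to the extent that, within a person, a high baseline on one day goes with a high 2-hour value that same day. If that link is weak, subtraction adds baseline noise to the contrast. A covariate lets the data set the slope; raw change fixes it at 1. With 30 participants and no power calculation behind that number, no stated margin covers the lost precision.

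**Working it through.** **Inputs from the documents.** 30 participants (Study Population), three sessions each (Study Design and Procedures), baseline and 2-hour CSA at each session (Data Collection Form). There is no plan figure to reproduce, because the sample size is stated without an SD, effect size, significance level or power.

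**Inputs assumed.** Let k be the within-person SD of baseline divided by that of the 2-hour value. Let r be the within-person correlation of the two in the same session. The documents give neither. Normality and a two-sided 5% level are also assumed.

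**Step 1: same target.** Baseline precedes the drink and order is randomised. Without carry-over, the expected baseline is therefore the same for all drinks, and subtracting it leaves the mean drink contrast unchanged.

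**Step 2: variance.** Set the within-person 2-hour SD to 1.
- Raw change: 1 + k² − 2rk.
- Baseline-adjusted: 1 − r².
- Ratio: (1 + k² − 2rk)/(1 − r²) = 1 + (k − r)²/(1 − r²).

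**Step 3: cost of estimating the slope.** There are 30 × 3 = 90 observations. Error degrees of freedom are 90 − 30 − 2 − 2 = 56 with participant, drink and session effects, and 55 with the covariate. The expected variance cost of the covariate is 1 + 1/(56 − 2) = 1.0185. The t quantiles are 2.0032 (56 df) and 2.0040 (55 df).
- Net variance ratio = [1 + (k − r)²/(1 − r²)]/1.0185.
- Net interval ratio = √(net variance ratio) × 2.0032/2.0040.

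| k | r | 1 + (k − r)²/(1 − r²) | Net variance ratio | Net interval ratio | Effective N of 30 |
|---|---|---|---|---|---|
| 1 | 0 | 2.000 | 1.964 | 1.40 | 15.3 |
| 1 | 0.5 | 1.333 | 1.309 | 1.14 | 22.9 |
| 1 | 0.75 | 1.143 | 1.122 | 1.06 | 26.7 |
| 1 | 0.9 | 1.053 | 1.034 | 1.02 | 29.0 |
| 0.5 | 0 | 1.250 | 1.227 | 1.11 | 24.4 |
| 0.5 | 0.25 | 1.067 | 1.047 | 1.02 | 28.6 |
| k = r | | 1.000 | 0.982 | 0.99 | 30.6 |

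Effective N is 30 divided by the net variance ratio. On variance, adjustment loses only when (k − r)²/(1 − r²) < 1/54. At k = 1 that means r above 53/55 = 0.964; at k = 0.5 it means r between 0.37 and 0.61.

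**Step 4: two open outcomes.** The correlation between the 2-hour contrast and the change contrast is (1 − rk)/√(1 + k² − 2rk). At k = 1 this is 0.707, 0.500 and 0.224 for r = 0, 0.5 and 0.9, so the two can disagree in a single trial. With no drink effect, the chance that at least one is significant for one additive-versus-black-coffee comparison is 1 − P(|Z₁| < 1.96, |Z₂| < 1.96). That gives 8.3%, 9.1% and 9.6% at k = 1, and 7.1%, 7.3% and 6.7% at k = 0.5, for the same three values of r. Over k from 0.5 to 1.25 and r from 0 to 0.9 the range is 6.7% to 9.7%.

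**Step 5: simulation check.** This used 8,000 three-period crossovers per cell, n = 30, no drink effect. For k = 1 with r = 0, 0.5 and 0.9, then k = r = 0.5:
- Interval ratios: 1.40, 1.14, 1.02 and 0.99.
- At least one outcome significant: 8.5%, 9.2%, 9.5% and 7.1%.
- Each single analysis rejected in 4.7% to 5.3% of trials.

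**The case against.** The strongest reply is that the Objectives section states an aim and Data Analysis says how it will be met. The pre-drink scan is called a baseline and each person is their own control, so change is a natural way to put the aim into practice. Both measures estimate the same contrast, and only one between-arm test is planned. This stands as far as it goes: a reader might infer that the trial answers the wrong question or is biased, and the documents do not support that. It does not settle which result is the main one, because the stated primary objective gives equal cover for a comparison of 2-hour volumes.

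A second reply is that subtraction already adjusts for baseline. That is correct, and it would be wrong to say the plan ignores the baseline. What is absent is an estimated slope. At k = 1 change is even more precise than unadjusted 2-hour volume once r exceeds 0.5, since its relative variance is 2(1 − r).

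A third reply is that the precision loss rests on k and r, which nobody can read from the protocol. This also stands. The 40% figure requires no same-session correlation at all, and the loss may be small.

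Finally, a reader might take 7-10% as the plan's false-positive rate. It is not. It arises only if both measures are tested and the significant one is reported; nothing in the documents describes that conduct.

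**Conclusion.** The point holds as a matter of alignment and efficiency. The mismatch between the objective and the planned comparison, and the lack of a designated primary outcome, are plain on the page. Using raw change in place of a baseline-adjusted comparison can widen each additive-effect interval by anything from about 2% to about 40% at k = 1 over r = 0.9 down to 0. When k is close to r, it instead narrows the interval by up to about 1%. The possible gain from adjustment is therefore much larger than its possible cost, but its size in this trial is unknown. The open choice of outcome is secondary: 7-10% is an upper bound on the error rate for one comparison, under conduct that is assumed. The figures rest on assumed k and r, approximate normality, complete data and no carry-over. It should be fixed because the remedy is cheap, not because any stated number is wrong.

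**What to change.** In Data Analysis, name predicted gastric volume at 2 hours as the single primary outcome, matching the Objectives. Compare drinks in a linear model with fixed participant, drink and session (period) effects and that session's baseline volume as a covariate. Report each additive-versus-black-coffee difference with its 95% confidence interval, and keep raw change as a supporting summary.

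If the sponsor prefers change as primary, say so in both sections and include the same covariate. The drink contrast is then identical, because moving the baseline from one side of the equation to the other only shifts its slope by 1. In simulation the largest discrepancy was 1.5 × 10⁻¹⁵.

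A participant's mean baseline need not be added. With fixed participant effects it is absorbed, even when sessions are missing: the design rank is 30 + 2 + 2 + 1 = 35 with or without it. It is relevant only if the participant effect is random.

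The cost is a few sentences, one error degree of freedom (56 to 55 with complete data) and intervals about 1% wider at worst. All the data needed are already on the form.
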